# Visit 2 (V2):

At the second visit (scheduled 2-3 weeks later), but before seeing the dentist or other dental team member, self-reported data will be collected on: self-assessed oral health data and oral health behaviours in the areas listed on the message card (given at the first visit) using an item stem of 'Since my last appointment I have..'. This will be followed by questions oral hygiene, diet and smoking behaviours as repeated measures from Visit 1. A set of EPPM items related to perceived susceptibility to risk of negative oral health outcomes will also be repeated.

A second QLF will be taken for all patients (none of these will be given to patients – they will be used to measure clinical outcomes).

At this appointment dentists or other team members will take another BPE score.

Visit 3 (V3): (scheduled 2-3 weeks after visit 2 (V2)), Self–assessed oral health and selfreported behaviour data collected on V2 will be repeated and a third QLF photograph taken to provide clinical (objectively verified data) on behaviour change.

At this appointment dentists or other team members will take another BPE score.

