WTP will be elicited using a shuffled payment card method, where a range of values are shown to the patient one at a time in a random order (Smith, 2006). The participant then decides for each value whether they are willing to pay the amount, unwilling to pay it or unsure. This then leaves a range between the lowest value that the participant is unwilling to pay and the highest value that they are willing to pay. The patient will then be asked to name the value between (and including) these values that would be the maximum they would be willing to pay. The decision for each card therefore is similar to a dichotomous choice (as recommended by Arrow and Solow, 1993)), but the whole process finishes with an open ended question. This approach minimises some of the problems associated with using either one of these methods on their own, such as starting point and range bias and making the cognitive task too difficult. Where participants give a zero value, they will be asked to identify the reason for the zero valuation from a range of options presented verbally and on a card. This will allow zeros to be later classified as true zeros or protest responses.

Baseline QLF photographs will then be taken of all patients to measure plaque levels. The patients will then brush their teeth and a second QLF photograph taken to measure tooth mineralisation. At this stage there will be no disclosure of the photograph to patients.

Patients will then have their dental check-up appointment (which will include a BPE examination). The dentist will open the randomisation envelope and patients will then be given their own personal risk information according to the randomisation schedule: either 1) Verbal only information (Model 1) or 2) Verbal information supported by a printed copy of the patients' oral health and risk of disease displayed as a traffic light (Red, Amber or Green), (Model 2) or 3) Verbal information supported by the QLF photographs taken earlier.

In the QLF arm the dentist will discuss the images with the patient in an electronic form on a Tablet PC. These patients will be offered an e mailed electronic image and/or a printed copy of the most meaningful image (either plaque or mineral loss) in a credit card size. A record will be made if an electronic image is sent. In the Traffic Light arm patients will be given a

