Formation of a 'normal' carious lesion takes at least six months (Ekanayake & Sheiham, 1987), with measurement of caries incidence using visual examination of teeth therefore only possible as a clinical outcome if follow up is extended over a significant time period. With the naked eye it is difficult to detect mineral loss in a short follow up period time because decay has to be fairly well advanced (at least 15% of mineral lost) before it can be seen by eye, usually as a white spot on the tooth. QLF extends detection of tooth mineral loss from 15% down to 0%. Thus demineralisation and remineralisation is detected in a matter of weeks. Brochner et al (2011) show significant regression of white spot lesions in four-weeks in patients where post orthodontic white spots were treated with preventive agents. Many other studies report similar findings. QLF thus provides an alternative, timely and more sensitive method for detection and measurement of early caries lesions than visual methods (De Josselin de Jong, 1995). As teeth demineralise there is a loss of fluorescence due to the increase in tooth porosity which in turn leads to a decrease in the refractive index of the carious lesion. Software allows changes in fluorescence of dental enamel to be quantified into mineral content. Detecting early caries is important because this gives an early indication of the likelihood of developing larger lesions, but at a stage where preventive behaviour can still lead to tooth remineralisation. Because QLF allows both mineral loss and gain to be quantified it is particularly useful for measuring early impacts of preventive interventions. Presence or absence of lesions will be scored on a per-surface base in each patient, using 3 photographs of buccal/labial tooth surfaces (one anterior image and right/left posterior images), producing data on percentage of surfaces affected for each patient. Data will also be recorded on severity where lesions are present, with  $\Delta Q$  denoting the product of the fluorescence loss and area over the demineralised lesion.

iii) Measurement of plaque using QLF (V1,V2,V3)

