## Comparing clinical outcomes between the three intervention arms

Comparison of QLF outcomes between the three groups will use a repeated measures mixed model approach. These models allow for analysis of multiple measurements within each participant. In this case each QLF outcome will be measured at three time-points. The first time-point is the baseline measurement, and the measurement taken here will be used as a covariate in the final model. The repeated measures approach allows us to analyse both follow-up measures (V2 and V3) together, while adjusting for the correlation of repeated measurements within participants. Using a mixed model approach, rather than a repeated measures ANOVA, allows for flexibility in the event of missing data, and can adjust for multiple covariates in the model. If there is a high level of missing data, a multiple imputation approach will be used to assess the robustness of the results. Using all the data which is available, 5 complete case data sets will be imputed, and each analysed in the same way. The results can then be combined, and compared with the analysis excluding missing data, to assess whether this would be likely to change the overall conclusions.

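### The brush-then-rephotograph sequence is written for Visit 1 only, so the lesion outcome at Visits 2 and 3 is not, as written, the same measurement as its baseline

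*Protocol*

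**What the plan says.** The Protocol's Procedures section sets out two imaging states at Visit 1. First, "Baseline QLF photographs will then be taken of all patients to measure plaque levels". Then: "The patients will then brush their teeth and a second QLF photograph taken to measure tooth mineralisation". The check-up follows.

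The Visit 2 text provides one QLF step: "A second QLF will be taken for all patients". The Visit 3 text provides "a third QLF photograph taken to provide clinical (objectively verified data) on behaviour change". Neither mentions brushing or a pair of images.

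The Measures section (6. Clinical Outcomes) nevertheless schedules both QLF outcomes at all three visits. Item ii covers early caries lesions at V1, V2 and V3, and item iii reads "iii) Measurement of plaque using QLF (V1,V2,V3". The section on comparing clinical outcomes between the arms adds: "In this case each QLF outcome will be measured at three time-points". It makes the first measurement the covariate and models the Visit 2 and Visit 3 values together.

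**The concern.** By having patients brush between the two Visit 1 images, the protocol treats plaque and mineralisation as needing different tooth conditions. A single imaging state at follow-up can match the Visit 1 condition for one of the two outcomes, not for both. On the literal text the follow-up images are unbrushed, so plaque matches its baseline and lesions do not.

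The lesion outcomes at stake are the percentage of affected surfaces and the severity measure ΔQ. QLF data are part of the trial's objective evidence on behaviour change, beside self-report. An imaging state that was never captured at follow-up cannot be recovered afterwards. The multiple imputation named in the protocol would have no observed brushed follow-up images to draw on if none were taken in any patient.

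**Working it through.** **The one related figure in the plan.** The sample size section states that 133 per group detects a PPI difference of 3.5 with SD 10, 80% power and a 0.05 level (two-sided assumed).

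- Standard error of the difference: 10 × √(2/133) = 1.226.
- Smallest difference detectable at 80% power: 1.226 × (1.960 + 0.842) = 3.44.
- Power at 3.5: Φ(3.5/1.226 − 1.960) = Φ(0.894) = 0.814.

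The statement reproduces. It concerns plaque and contains no baseline or repeated-measures term, so the imaging sequence at follow-up does not alter it.

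**Tooth condition by outcome and visit, following the text as written.**

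| Outcome | V1 | V2 | V3 | Same basis? |
|---|---|---|---|---|
| Plaque (PPI, red fluorescence area) | before brushing | one QLF step, no brushing stated | one QLF step, no brushing stated | yes, if unbrushed |
| Early lesions (% surfaces, ΔQ) | after brushing | same step as plaque | same step as plaque | no |

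If a practice instead has patients brush before the single follow-up step, the last column reverses: lesions match and plaque does not. With one state per visit, no reading gives two matches.

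**What this does to the lesion analysis.** Write the lesion score read on unbrushed teeth as the brushed score plus a shift δ.

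1. *Change from baseline.* Follow-up minus baseline equals true change plus δ. Raw change therefore mixes procedure with mineral change.
2. *Covariate.* Adjusting for baseline leaves a residual variance proportional to 1 − r², where r is the correlation of baseline with follow-up. Measuring the two in different states would be expected to lower r and so lose precision.
3. *Arm comparison, constant δ.* (μ_A + δ) − (μ_B + δ) = μ_A − μ_B. A fixed shift cancels.
4. *Arm comparison, δ depending on plaque P at follow-up.* The contrast becomes μ_A − μ_B + [δ(P_A) − δ(P_B)]. The bracket is zero only if follow-up plaque does not differ by arm or does not affect lesion reading. Plaque is itself an outcome that the arms may change, and neither randomisation nor the Visit 1 covariate removes a difference that arises after randomisation.

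The documents give no value for δ, its relation to plaque, or r. Steps 1 and 2 follow from the text. Step 4 is a possible mechanism of unknown size.

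**The case against.** The strongest reply is that the Visit 2 and Visit 3 text is silent on brushing and does not exclude it. The words second and third there seem to count visits, because a second photograph has already been taken at Visit 1. The Visit 2 text refers to its images in the plural, and a lesion assessment uses three views, so one QLF may mean a whole session. The Procedures heading also points to a flow diagram and a study crib sheet, which are not shown and may repeat the sequence. All of this stands as a reason not to say that the outcomes cannot be measured. It does not supply the missing step: the three views are anterior, right and left, not before and after brushing. The protocol wrote the sequence out for Visit 1, and four practices working from its follow-up text could settle the matter differently.

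A second reply is that every arm follows the same procedure. This stands for a fixed shift. It does not cover a shift that depends on plaque.

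Three stronger readings are tempting, and the documents support none of them.

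- *The lesion comparison between arms is biased.* That needs plaque to alter lesion scoring and to differ by arm at follow-up. Neither is quantified. Ratios built on the share of enamel left visible would need invented multipliers, and they would not fit an outcome scored as presence or absence per surface, since a partly covered lesion can still count.
- *Plaque is compromised too.* Under the literal unbrushed reading it is not. It is affected only where a practice brushes first.
- *BPE is affected.* At Visit 1, "Patients will then have their dental check-up appointment (which will include a BPE examination", after the brushing; at follow-up, "At this appointment dentists or other team members will take another BPE score", with no brushing stated. But BPE is a clinical score that does not come from the photographs, and nothing in the protocol indicates that recent brushing changes it.

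**Conclusion.** The point holds as a mismatch between the procedures and the outcomes they must supply. Two imaging states are specified at baseline and one at each follow-up visit, while two QLF outcomes are required at all three. Followed as written, follow-up lesions are read on unbrushed teeth and adjusted for a baseline read on brushed teeth. This distorts change from baseline and weakens the covariate, and it leaves open a dependence of lesion detection on follow-up plaque.

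The conclusion rests on taking the Visit 2 and Visit 3 text at face value. If the flow diagram or crib sheet already repeats the sequence, what remains is a wording gap in the protocol. The size cannot be derived from the documents. One secondary QLF outcome is affected on the literal reading. The PPI power statement and the primary outcome, willingness to pay, are untouched. It should be corrected, but it is not a must-fix.

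**What to change.** In the Visit 2 and Visit 3 procedures, state that the Visit 1 sequence is repeated: unbrushed QLF views, the patient brushes, brushed QLF views. In the clinical outcomes section, state that at every visit plaque is scored only from unbrushed images and lesions only from brushed images. Where a visit yields only one image set, use it for the outcome whose condition it matches and treat the other as missing. Bring the flow diagram and crib sheet into line if they differ.

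The cost is two short wording changes and a few extra minutes at each of the two follow-up visits for brushing and repeat photographs. The equipment and trained staff are already there, and no new assessor is needed.

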# Telephone follow up (F1, F2):

There will be a telephone follow up interview of all 400 patients 6 months and 12 months after V1 to gather further data on behaviour change outcomes (self-assessed oral health and oral health) in order to give a longer term measure of change in behaviour.

# Measures

## 1. Explanatory variables

a) Patients' characteristics: the following data will be collected at V1

## Demographic characteristics

- Socio-economic status measured by area classification: Postcode allocated to IMD quintile
- Whether the patient is exempt from dental charges or not.
- Gender: Male, Female
- Age: in years
- Education: The highest level of education given in 5 categories 1= GCSE or NVQ level 1 or similar, to 5= postgraduate degree.
- Employment status: 1=employed or self-employed full-time, 2=employed or selfemployed part-time, 3=unemployed at the moment, 4= full-time education
- Household Income (before deductions e.g. income tax): according to 9 categories given as weekly or yearly amounts, ranging from 1= £0 to 9= over £52,000 per year

Measures of education and income will be according to the Office for National Statistics (2015) standard ways of categorising households according to demographics.

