concerns about a possible age-based digital divide (Tang & Lansky, 2005), and that the use of e-health may widen ethnic and socio-economic health inequalities (Hsu et al, 2005). Our research then asks the question: 'What is the cost and value of purely verbal information on oral health and risk of disease, compared to information based on a Traffic Light presentation information or QLF images sent to mobile phones?'

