#### **Participants**

The study will involve 400 adult patients (aged 18 years or older), (100 in each of the four dental practices), who have been identified clinically as having high/medium oral health need/ risk of disease. We will use the nationally developed algorithm categorising patients as Red/Amber to define patients who are eligible for inclusion in the study. We will include patients will low literacy, but exclude patients who require an interpreter for dental care.

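### The employment-status item has no code for retired, long-term sick or disabled, home-caring or other patients, although all adults are eligible, so it is unreliable as an explanatory variable in the secondary WTP analyses

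*Protocol*

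**What the plan says.** The protocol, under Measures, Demographic characteristics, lists the employment codes as "1=employed or self-employed full-time, 2=employed or selfemployed part-time, 3=unemployed at the moment, 4= full-time education". All four are written out, and there is no residual category.

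The education item just above is given by its end points only: "Education: The highest level of education given in 5 categories 1= GCSE or NVQ level 1 or similar, to 5= postgraduate degree". The same section then ties two items to a national standard: "Measures of education and income will be according to the Office for National Statistics (2015) standard ways of categorising households according to demographics". Employment status is not among them.

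On entry, the Participants section says "The study will involve 400 adult patients (aged 18 years or older", with no upper age limit, and adds "We will include patients will low literacy, but exclude patients who require an interpreter for dental care".

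Employment status and education are self-reported at Visit 1 (Procedures) and stand in the protocol under Explanatory variables. Objective 5 asks how preference for the forms of information differs between demographic, behavioural and psychographic groups. The WTP part of the Phase 2 Analysis plans OLS or Tobit regressions of WTP on dental and demographic factors.

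**The concern.** A code list for an explanatory variable should give every eligible patient one correct answer. This one does not. A retired patient, a patient unable to work through illness or disability, and a patient caring for home or family fit none of the four codes. The nearest is code 3, and the alternative is a blank.

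Either outcome weakens the variable. If these patients go into code 3, a coefficient labelled unemployed describes a mixture of people outside work for different reasons. If they are left blank, the missing values are concentrated in particular groups rather than spread at random.

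The Background gives differences between patient groups as a motive for the study, including "concerns about a possible age-based digital divide" and socio-economic inequality, so the demographic analysis is a stated objective. The gap also arises when the data are collected. Once a retired and an unemployed patient share a code, no analysis plan can separate them from that item.

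**Working it through.** No figure in the protocol (sample size, power or detectable difference) depends on these codes, so there is nothing to reproduce. The check sets the sections side by side and then illustrates the possible size.

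**Step 1. Is the employment list complete as printed?** Education and income are given as ranges, from a lowest to a highest category. Employment is not: codes 1, 2, 3 and 4 are each spelled out. It therefore reads as the full list and not as an abbreviation.

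**Step 2. Are uncoded patients eligible?** Yes. Participants sets a minimum age of 18 and no maximum, and nothing in that section restricts entry by work status.

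**Step 3. Does the cited national standard fill the gap?** No. The sentence covers education and income only.

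**Step 4. Does the education item have the same gap?** It may. The lowest printed level is already a qualification, and patients with low literacy are deliberately admitted. But only the two end points are printed, the lowest level allows for similar qualifications, and the item refers to a standard that is not reproduced. This needs checking and is not established.

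**Step 5. Illustrative size.** The protocol gives no shares, so both inputs are assumptions: f, the share of the 400 patients with no valid employment code, from 5% to 40%; and u, the share truly unemployed, from 5% to 10%.

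- If all uncoded patients are put in code 3, the share of code 3 that is not unemployed is f / (f + u).
- If all are left blank and a regression keeps complete cases only, standard errors rise by the factor √(400 / (400 − 400f)).

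| f | Patients without a code | Share of code 3 not unemployed, u = 10% | Same, u = 5% | Complete cases | Standard-error factor |
|---|---|---|---|---|---|
| 5% | 20 | 33% | 50% | 380 | 1.026 |
| 10% | 40 | 50% | 67% | 360 | 1.054 |
| 20% | 80 | 67% | 80% | 320 | 1.118 |
| 30% | 120 | 75% | 86% | 280 | 1.195 |
| 40% | 160 | 80% | 89% | 240 | 1.291 |

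For f = 20%: 0.20 / (0.20 + 0.10) = 0.67, 0.20 / (0.20 + 0.05) = 0.80, and √(400 / 320) = 1.118. The two columns of consequences are opposite extremes. In practice patients would be split between code 3 and blank.

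**The case against.** The strongest reply is that little depends on this item. The primary comparison of WTP between the information forms uses neither employment nor education, and the same holds for the sample size, the randomisation and the clinical comparisons as described. The factors that the Background names are largely measured elsewhere: age in years, deprivation quintile, nine income bands, exemption from charges, and literacy by REALM-R. Differences in age, income and charge status within a mixed code 3 can be adjusted for. All of this stands, and it keeps the point secondary.

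A reader might infer that retired patients will be dropped from the WTP models. The document does not support that. It does not list the covariates, does not say that employment status must enter, and does not specify complete-case deletion. Those choices may properly be made in a statistical analysis plan that is not shown. The standard-error column above is therefore conditional.

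A reader might also infer that patients without qualifications cannot be recorded at all. With only the end points of the education scale printed, that cannot be said.

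Finally, the Visit 1 form is not in the document, and Piloting of methods mentions a socio-economic classification based on occupation, which might capture retirement. However, that classification does not reappear in the Visit 1 procedures or under Demographic characteristics, where socio-economic status is measured by area. It does not repair the four codes that the protocol fixes.

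**Conclusion.** The point holds for employment status. As printed, the list is complete and omits groups that entry admits, so the variable cannot be trusted to separate unemployed patients from others outside work. The effect is confined to secondary work: the WTP analyses by demographic group under objective 5. The primary WTP result is not threatened, and the recorded substitutes limit the loss without restoring the missing distinction.

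The size cannot be fixed from the document. Under the assumed ranges, between 33% and 89% of code 3 would not be unemployed if every uncoded patient went there. If instead all were left blank and then excluded, standard errors in the affected models would rise by about 3% to 29%. These are illustrations at two extremes and not estimates for this trial.

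For education, the conclusion is only that the lowest level needs checking. Since the remedy costs almost nothing and the detail is hard to recover after Visit 1, the change should be made.

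**What to change.** Before enrolment, add four response options to the employment item: retired, long-term sick or disabled, looking after home or family, and other. If cells are sparse, the regression can combine them into a category separate from unemployed. The original answers remain available.

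Check the education item on the Visit 1 form. If it has no level for no formal qualification, add one below the present code 1.

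The cost is four extra tick boxes, or five if the education level is needed, and somewhat smaller cells in the demographic regressions. Sample size, visits and the primary analysis are unchanged.
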